9.3 POTENTIAL BENEFITS TO SUBJECTS

Subjects in the study who receive the intervention may benefit by having more intensive support during the ED to home transition.

9.4 ALTERNATIVES TO PARTICIPATION

Subjects may elect to not participate.

10 CONFIDENTIALITY OF DATA AND INFORMATION STORAGE

While the study is underway, all data will be identifiable. However, we will take many actions to maximally protect the data and mitigate the risk of breach of confidentiality.

1. For data collection purposes, identifiers will be used to label all collection forms. These forms will be initially stored in secure URMC or UW Department of Emergency Medicine offices and will be destroyed once the data are uploaded into REDCap the electronic data management system.
2. All data will be maintained in REDCap, an electronic data management system application on a UW Madison School of Medicine and Public Health server and maintained by its IT staff.
3. Only the PI and research staff with direct reasons for access will be allowed to access the data.
4. No identifiable data will be kept from those subjects who were ineligible for the study or who chose not to enroll.

5. For analysis procedures, all subjects will be assigned an automatically generated identification code in the RedCap system. This code will be used for data linkage purposes during analysis. Data will be reported as group data so that no individual could be identified.
6. After study completion, direct identifiers will be removed from the datasets. Only an auto-generated REDCap assigned subject number will be used for data linkage purposes. These limited datasets will be retained on limited access, secure UW servers.
7. Limited analysis datasets will be kept for 7 years after completion of the study, or longer to allow for secondary analysis after the study is complete.
8. All members of the study team will complete either a UW or URM CITI and HIPAA training.

11 RESEARCH INFORMATION IN MEDICAL RECORDS

We will not add research information in medical records.

12 DATA ANALYSIS AND MONITORING

12.1 SAMPLE SIZE DETERMINATION

This study is designed to have adequate power to test the primary hypotheses that the CTI will result in lower odds of repeat ED use within 30 days of discharge compared to the control group (Hypothesis 2B). Based on published data, we expect 20% of the subjects in the control group to have at least 1 repeat ED visit within the 30-day follow-up period. In order to detect a 5% absolute decrease in the frequency of repeat ED visits with 80% power using a Chi-square test at a two-sided significance level of 5%, we will need 860 subjects per group. We anticipate approximately 25% attrition over the 30-day follow up period. As such, a final sample size of 1200 subjects in each group will be recruited for participation. We also calculated the minimum detectable effect size testing individual biomedical and psychosocial factors predicting repeat ED visit in Aim 4 for intervention group only. With an expected 15% baseline proportion of repeat ED visit, the sample size of 860 in the intervention group will have 80% power to detect an odds ratio (OR) of 1.3 per standard deviation of a normally distributed predictor. Similarly, 80% power is available to detect an OR ranging from 1.6-1.7 for a binary predictor prevalent in 30-50% of subjects.

We will also have to adjust for clustering by site in most of the analyses below.

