4. CHARACTERISTICS OF THE RESEARCH POPULATION

4.1. SUBJECT CHARACTERISTICS

Number of Subjects: We propose to enroll 2400 ED patient subjects into the study, with 1200 of the enrollments coming at UW and 1200 at UR Medical Center-Strong Memorial Hospital or UR Medical Center-Highland Hospital. Of the 2400 subjects, 1200 will be randomized to the intervention group and 1200 to the control group. We will also enroll up to one informal caregiver per ED patient, resulting in up to 2400 additional subjects. Thus, the total number of subjects potentially enrolled in this study is 4800.

Gender and Age of Subjects: All patient subjects will be age 60 years and older, as this is a concern of the older adult population. Both men and women will be enrolled.

Informal caregiver subjects must be age 18 or older, and will be either male or female, depending on who is identified by the patient subject.

Racial and Ethnic Origin: Individuals of all races and ethnicities will be included.

Vulnerable Subjects: Older adults are the focus of this study as these problems are not as prevalent for younger individuals; thus evaluating transitional care for them is of likely little benefit and any developed knowledge may not be translatable to older adults. We will implement safeguards to protect this population:

1. The study staff will not be directly providing ED clinical care to the participants, thus eliminating any potential coercion.
2. Decisional capacity will be evaluated by the RA obtaining consent to ensure that participants understand the risk and benefits of the study before obtaining informed consent, unless the Health Care Power of Attorney has already been activated. The decisional capacity evaluation process that will be used has been approved by the UR IRB. It assesses the potential subject's understanding of the study. This process is more conservative than the UW IRB policy "Research with Adult Participants Lacking Capacity to Consent" (Section II) as all subjects will be tested in this minimal risk study. The PI ([name], emergency medicine), co-I ([name], geriatrician), and project director ([name], psychology degree, extensive community health/social work experience working with vulnerable populations) will ensure that all RAs who conduct the capacity assessment will be fully trained.

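### Section 12.1 states that 860 per group gives 80% power for 20% versus 15%; the test it names needs 906, and 860 gives about 78%

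*Combined protocol and SAP*

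**What the plan says.** Section 12.1 powers the trial on Hypothesis 2B, the odds of repeat ED use within 30 days. The assumed control rate is given as "we expect 20% of the subjects in the control group to have at least 1 repeat ED visit within the 30-day follow-up period", and the target is to "detect a 5% absolute decrease in the frequency of repeat ED visits". The requirement then reads: "80% power using a Chi-square test at a two-sided significance level of 5%, we will need 860 subjects per group".

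The section next allows for loss to follow-up ("We anticipate approximately 25% attrition over the 30-day follow up period") and concludes that "a final sample size of 1200 subjects in each group will be recruited for participation". Section 4.1 confirms equal allocation: "Of the 2400 subjects, 1200 will be randomized to the intervention group and 1200 to the control group".

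The same section reuses the figure for Aim 4: "With an expected 15% baseline proportion of repeat ED visit, the sample size of 860 in the intervention group". This also confirms that the intervention-group rate behind the calculation is 15%.

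Appendix A, section 2.0, plans no interim analysis, so no alpha is spent before the final test.

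**The concern.** Every input needed to reproduce the sample size is stated, and the stated result does not come out. The 860 is calculated before attrition, so the word approximately, attached to the 25%, cannot explain it. Section 12.1 also says that most analyses must adjust for clustering by site. No allowance for this appears in the calculation, and it gives no reason for a figure below 906.

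The figure matters because it is presented as the evaluable number that protects the primary hypothesis, so it is the natural floor for judging retention. Taken at face value, 1200 recruited against 860 needed would tolerate a loss of 1 − 860/1200 = 28.3%, more than the 25% planned. If evaluable numbers did fall to 860, the team would think it still had 80% power when it had about 78%.

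**Working it through.** **Inputs.** From section 12.1: p₁ = 0.20 (control), p₂ = 0.20 − 0.05 = 0.15, two-sided α = 0.05 (z = 1.960), power 80% (z = 0.8416), chi-square test. From section 4.1: allocation 1:1. The mean rate is p̄ = 0.175.

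**Required number, uncorrected chi-square test (pooled variance under the null):**

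n = [1.960 × √(2p̄(1 − p̄)) + 0.8416 × √(p₁(1 − p₁) + p₂(1 − p₂))]² / (p₁ − p₂)²

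- √(2 × 0.175 × 0.825) = 0.53735, and × 1.960 = 1.0532
- √(0.16 + 0.1275) = 0.53619, and × 0.8416 = 0.4513
- n = (1.0532 + 0.4513)² / 0.0025 = 2.2634 / 0.0025 = 905.4, so **906 per group**

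This is 46 more than 860 (46/860 = 5.3%).

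**Attempts to reproduce 860 by other methods:**

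| Method | n per group |
|---|---|
| Unpooled variance, two-sided | 902.6 → 903 |
| Arcsine, two-sided | 902.3 → 903 |
| Pooled variance in both terms, two-sided | 906.5 → 907 |
| Log odds ratio, two-sided | 911.8 → 912 |
| Continuity-corrected, two-sided | 945 |
| One-sided, uncorrected | 714 |
| One-sided, continuity-corrected | 753 |

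None lies within 3% of 860 (834 to 886). The number is close to what a 78% power target would give (862), but the plan does not state that target.

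**Power at the relevant numbers**, from power = Φ[(0.05 − 1.960 × se₀)/se₁], where se₀ = √(2p̄(1 − p̄)/n) and se₁ = √(0.2875/n). For n = 860, se₀ = 0.018324 and se₁ = 0.018284, so power = Φ(0.770) = 77.9%.

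| Evaluable per group | Power (formula) | Power (exact enumeration) |
|---|---|---|
| 860 | 77.9% | 78.1% |
| 900 | 79.8% | 79.9% |
| 906 | 80.0% | 80.2% |

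**From evaluable to recruited:**

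- 860 / (1 − 0.25) = 1147, and 860 × 1.25 = 1075; neither is 1200.
- 1200 × 0.75 = 900, not 860.
- 906 / 0.75 = 1208, which is 8 per group above the plan.

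**Aim 4.** The smallest detectable odds ratio per standard deviation is exp√[(1.960 + 0.8416)² / (n × 0.15 × 0.85)]. This is 1.307 at n = 860 and 1.299 at n = 900. Both round to the 1.3 stated in the plan.

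**The case against.** The best defence is that the trial is protected by the number recruited, and that number is nearly right. With 1200 per group, 906 remain evaluable at 24.5% loss, which is within any reasonable reading of an approximate 25%. At exactly 25%, power is 79.8%, which rounds to 80%. This stands, and it is why the point is a correction to the text and not a call for more subjects.

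Second, not all attrition need cost the primary outcome. Section 3.2 draws health care use from administrative data as well as surveys, and continues record review for subjects who only stop contact. Section 4.2 requires a PCP affiliated with a study site. The plan does not say how many outcomes this would save, so only a range can be given. Power would be 82.3% with 20% of outcomes lost (960 per group), 86.4% with 10% lost (1080) and 89.7% with none lost (1200). This also stands. The absence of reserve applies only if the full 25% lose the outcome.

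Third, going from 1147 to 1200 could be deliberate rounding up. That is possible, although the plan does not say so, and the mismatch is secondary to the error in 860 itself.

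Fourth, the Aim 4 statement is correct for the 860 it names, and 860 is the more cautious input. That is so; changing it serves consistency only.

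Finally, no rule in the plan uses 860 as a trigger, and reaching it would take 28.3% loss. That limits the harm but does not make the figure right. None of these points supplies a calculation that yields 860 at 80% power.

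**Conclusion.** The concern holds. On the plan's own inputs the uncorrected chi-square test needs 906 per group for 80% power, and 860 gives 77.9% (78.1% exact). The understatement is 46 per group, or about 2 percentage points of power.

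The planned 1200 per group with 25% loss of the primary outcome leaves 900 and 79.8% power (79.9% exact), so the trial is not materially underpowered on these assumptions. The error lies in the stated requirement and in the apparent margin that it creates.

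This rests on rates of 20% and 15%, 1:1 allocation, no interim look, no continuity correction (the plan specifies none) and no allowance for site clustering. A continuity-corrected test would need 945 evaluable, or 945/0.75 = 1260 recruited, per group.

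**What to change.** Correct two sentences in section 12.1, along these lines: *906 evaluable subjects per group are needed for 80% power with a two-sided 5% chi-square test of 20% versus 15%. Recruiting 1200 per group with 25% attrition leaves 900 evaluable per group and gives 79.8% power.*

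For consistency, the Aim 4 sentence could use 900 in place of 860; the detectable odds ratio stays at 1.3 per standard deviation. This part is optional.

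The cost is a text edit and a very slightly less favourable power statement. Enrolment, design and analysis stay as they are.

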12.2 PLANNED STATISTICAL ANALYSIS

Through the analytic methods used in Aims 2 and 3, we will assess differences between groups related to process outcome measures (Aim 2) and will assess the effectiveness and cost-effectiveness of the ED-to-home CTI (Aim 3). In Aim 4, we will identify predictors of repeat ED use among intervention group subjects. We will characterize of our study sample using descriptive statistics and corresponding measures of variation. We will assess for differences between groups at baseline despite randomization in key characteristics (e.g., demographics, comorbidities) using t-tests for continuous variables and Chi-square tests for categorical variables, using Fisher's exact test where appropriate. These comparisons will enable the identification of covariates to be controlled in our multivariable analyses. If distributional assumptions associated with a particular statistical procedure are violated, we will use appropriate transformations or non-parametric alternatives. Primary analyses will be performed under the intent-to-treat principle, keeping subjects in the group to which they were originally randomized, regardless of compliance or adherence to study procedures. We will conduct sensitivity analyses among subjects who complete all study procedures to evaluate the effect of the intervention among those who complete all study-related procedures. Hypothesis-driven comparisons will be made to control the family-wise type I error rate at 0.05 (two-sided) for the primary hypothesis.

Caregiver Subject Analysis: Although not an original aim of the study, we have obtained permission from the NIH and will perform a limited analysis of caregiver activation. This was only recently added to

the CTI. To compare the caregiver activation between the control and intervention groups, we will administer the FCAT. The FCAT will be scored as 1-6 points per question, for a score ranging from 10-60. We assume that 30% of participants will have caregivers with them, the average score will be 30, and we will look for a 5 point difference. Our sample size will allow a power of >0.8 for a t-test ($\alpha=0.05$).

Hyp 1A: More program participants will demonstrate understanding of their ED discharge instructions, red flags that indicate a worsening of their condition, and how to respond to the red flags three days after ED discharge.

Hyp 1B: More program participants will implement medication changes made in the ED within three days of ED discharge.

Hyp 1C: Program participants will have shorter time-to-follow-up with their primary care physicians.

Hypothesis 1A & 1B: Binary outcomes such as patients' understanding of their ED discharge instructions, red flags and how to respond, and accurate implementation of medication changes, will be compared between intervention and control group using chi-square tests. Estimates of differences between study groups and associated 95% confidence intervals will be provided overall and by study site. A separate multivariable logistic regression model will also be fitted for each of the outcome variables in hypotheses 1A and 1B. This will allow us to evaluate the effect of the intervention on each of these outcome variables while controlling for potential confounding variables, if necessary. **Hypothesis 1C:** Time-to-follow-up visit with primary care physicians will be compared between groups using the Log-Rank Test. Cox regression model will be fitted to compare the survival function after adjusting for potential confounding variables such as demographics, comorbidities etc., if necessary. A hazard Ratio and 95% confidence interval will be estimated. Because we have the issue of competing outcomes present (rehospitalization and follow up), we will have to account for it through the cumulative incidence function.⁷²

Hyp. 2A: Program participants will have increased patient activation 30 days after discharge.

Hyp. 2B: Program participants will have lower odds of repeat ED use within 30 days of discharge.

Hyp. 2C: Program participants will have lower estimated healthcare costs within 30 days of discharge.

Hypothesis 2A & 2B: To evaluate difference in subjects' self-care competency, Wallston scores will be compared between intervention and control groups using the Wilcoxon Rank Sum test. Any repeat ED use and the number of ED visits during the 30-day follow up period will be compared between intervention and control groups using the Chi-square test and ANOVA as appropriate. To adjust for potential baseline differences between intervention and control subjects, a multiple logistic regression model will be constructed with repeat ED use as the dependent variable, study intervention group as the primary independent variable, and any covariates that were found to be imbalanced at baseline in our bivariate analyses. Multicollinearity between predictor variables will be assessed using multiple correlations (variance inflation factors). We will use the log likelihood ratio to assess overall model fit. We will also check for overdispersion and use Generalized Estimating Equation (GEE) to provide robust estimates of standard errors. Possible interaction effects between the covariates will be inspected and stratified analyses will be performed if there are significant interaction effects. Standard diagnostic measures for logistic regression such as Pearson residual and deviance residual will be used to check the goodness-of-fit of the regression model assumptions and identify any outliers.

Hypothesis 2C: The proposed economic assessment considers the financial costs and benefits of the CTI. Consistent with standard terminology,⁷³ we define *financial benefits* for this study as the consequences of the CTI that are related to health services cost, expenses, salaries, revenues, and other fiscal issues. It is important to recognize that adoption of the CTI will include both fixed (e.g., implementation) and variable (e.g., dependent on units of care delivered/patients served) costs. Dissemination of the program will require additional resources to cover CTI implementation. Hence, we

include fixed and variable costs in our analysis while excluding costs associated with the research. We will evaluate the economic impact of CTI from the perspective of health care system/insurers, including both the cost of the CTI and the expected healthcare cost reduction due to altered use of ED, hospital, and office visits. Impact on direct healthcare costs (and hence analysis from the insurer perspective) will be most critical to the adoption and dissemination of this care model since insurance organizations (dominant stakeholders through control of payment), are unlikely to reimburse for CTI care unless they assess it as at cost-neutral or better.

The occurrence of events contributing to healthcare costs (e.g., ED visits) will be ascertained from clinical information systems at both health systems. We will estimate the following CTI expenses for the intervention group: hardware and/or software investments; maintenance costs; direct and indirect costs for training; personnel salary and benefit costs, etc. We will estimate the value of direct healthcare resources saved or expended, including both fixed and variable costs. We will use Medicare reimbursement schedules to assign costs to events because of their national scope, relevance to older populations, and alignment with the true costs of care rather than inflated costs or discounted insurance plan reimbursements. We will calculate total direct costs for each individual by taking the product of the costs per visit (price) and utilization by visit type, and summing across categories of utilization for that individual. We will then estimate unadjusted and adjusted incremental costs. The adjusted cost approach uses multivariable regression models to eliminate the effects of differences in population characteristics across comparison groups, if appropriate. To do so, we will estimate the program's monthly and annual costs using multivariable models and then will calculate the incremental cost of the CTI. All prices will be calculated in 2015 dollars. Using collected data, we will extrapolate the costs of running the program and expected benefits over 12-month period and annually. Finally, we will make economic projections of the program's financial sustainability and scalability. We will conduct a series of sensitivity analyses by modifying local wages, population case-mix and program effectiveness to estimate boundaries to program's sustainability and optimal operational conditions.

To test the hypothesis that individual in the treatment group will have lower health care costs within the 30-days of ED discharge, we will first calculate total direct costs for each individual by taking the product of the costs per visit (price) and utilization by visit type, and summing across categories of utilization for that individual. We expect to find that total health care expenditures will exhibit a right skewed distribution with no negative measures and a nontrivial number of zeros. Consistent with the literature, we will log transform total spending to generate a normal distribution and use the box cox and GLM family test to find the distribution to best in our data. We will use the recycled predications method to re-transform estimates back from the log scale and compare average health care spending in the treatment and control groups.

Hyp. 3A: Biomedical factors associated with repeat ED visits include increased age, increased number of comorbidities, impaired cognition, and limited functional status.

Hyp. 3B: Psychosocial factors associated with repeat ED visits include reduced social connectedness, increased anxiety symptoms, and increased depressive symptoms.

To evaluate the relationship between biomedical and psychosocial factors with the occurrence of repeat ED visits among intervention subjects we will conduct bivariate analyses between patient characteristics and the primary outcome measure (repeat ED visits within 30 days). To do this we will conduct bivariate analyses with potential predictor variables and the dependent variable (repeat ED use) using two sample t-tests for continuous variables or Chi-Square tests for categorical variables, using Fisher's Exact test where appropriate. We will then identify independent predictors of repeat ED visits by fitting a multiple logistic regression model with biomedical and psychosocial factors identified in the bivariate analysis as independent variables. Model fitting statistics such as Akaike's Information Criteria and difference in log likelihood will inform the development of the final regression model. Standard diagnostic measures such

as residual plots will be used to assess the goodness-of-fit of the regression model assumptions and identify any outliers.

Missing Data: Inference based on the proposed method is valid provided that missing data follows the missing completely at random (MCAR) assumption. However, the occurrence of missing data may depend on the observed response and such as missing at random (MAR) mechanism will generally bias the estimates. Sensitivity analysis will be performed to examine the MCAR assumption. If it is deemed to be severely violated, we will report treatment effects using weighted GEE that addresses the MAR mechanism.^{74,75} Biased estimates may arise if missing data does not follow the MAR mechanism, or non-ignorable non-response (NINR). Although unanticipated in this study, we will examine this potential NINR using the mixture model approach.⁷⁶

Future Planned Analysis: We are requesting to retain the data in an identified form for 10 years after completion of this study for future analyses of health care utilization and claims data from subjects' health insurance providers so as to understand if a paramedic coach reduces health care use and costs. We will keep the deidentified data indefinitely.

